6.6.1 Treatment discontinuation

1. The subject may discontinue treatment at will at any time.
2. Treatment may be discontinued at the discretion of the investigator due to a safety concern or if the subject is judged non-compliant with trial procedures.

Treatment must be discontinued if the following applies:

3. Adverse Event: If a subject reports symptoms which are considered unacceptable by the subject or the investigator, regardless of relationship to trial product, treatment must be discontinued
 4. Any other condition develops that is cited in exclusion criteria (except for development of diabetes mellitus during the course of the trial that can be controlled with standard therapy)
 5. Development of neutralising antibodies to NNC0195-0092 defined by 2 consecutive samples found positive for *in vitro* neutralising antibodies and an influence on PK as described in section [8.5.13](#). The investigator will be notified by the sponsor if a subject has had 2 samples positive for *in vitro* neutralising antibodies immediately after obtaining knowledge of the results.
 6. Pregnancy*
 7. Intention of becoming pregnant during the trial, including the extension period*
- *No DXA scans can be performed on these subjects

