8.3.3 Concomitant medication

A **concomitant medication** is any medication, other than the trial products, which is taken during the trial, from screening to the last follow up visit in the trial.

Details of any concomitant medication must be recorded at the first visit. Changes in concomitant medication must be recorded at each visit as they occur.

The information collected for each concomitant medication includes trade name or generic name, dose, indication, start date and stop date or continuation. For medications containing oestrogen also the route of administration must be recorded.

If a change is due to an AE, then this must be reported according to section [12](#). If the change influences the subject's eligibility to continue in the trial, the monitor must be informed.

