8.5.6 Fasting plasma glucose, fasting insulin, and HbA1c

Fasting plasma glucose, fasting insulin, and HbA1c tests will be assessed at screening and every 2 to 3 months throughout the trial (see section [2](#)). Subjects must be fasting 8 hours before sample collection, with only water allowed. If the subject comes to a fasting visit in a non-fasting state this needs to be recorded in the eCRF.

Rescue criterion for subjects diagnosed with diabetes mellitus before inclusion into the trial: If the HbA1c increases clinically significantly during the trial, the investigator should consider adjusting the anti-diabetic medication according to local practice.

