17.4.1.2 Safety endpoints

The following endpoints will be used to support the secondary objectives of evaluation of safety in both the main (up to week 35) and extension (up to week 88) trial periods:

- Incidence of adverse events, including injection site reactions
- Incidence of clinical technical complaints
- Occurrence of anti-NNC0195-0092 antibodies
- Changes from baseline in physical examination, ECG results and vital signs
- Changes from baseline in clinical laboratory test results including haematology, biochemistry, fasting glucose, fasting insulin, steady state beta cell function (%B) and insulin resistance (IR) (HOMA estimates), and HbA1c levels

Adverse events will be analysed using descriptive statistics. All adverse events with onset after the first administration of trial product and up until Week 34 will be included in the main trial period analysis. The adverse events will be summarised by treatment, MedDRA (Medical Dictionary for Regulatory Activities) system organ class and MedDRA preferred term. The descriptive statistics will include the number and percentage of subjects who experienced adverse events and the number of events. Adverse events will be listed by treatment and subject with information on severity, relationship to trial product and demographics. Adverse events with onset before first dosing will be reported in a separate listing.

All other safety endpoints will be analysed using descriptive statistics. Additionally, an exact logistic regression analysis on the event of experiencing at least one injection site reaction during the main trial period will be done with treatment, GHD onset type, sex, region, DM and sex by region by DM interaction as factors included in the model as factors and number of injections taken in the main trial period included as offset.

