Appendix 16.1.1

~~CONFIDENTIAL~~

Date:
Version:
Status:

27 November 2017
1.0
Final

Novo Nordisk

Global and country key Novo Nordisk staff

Attachments I and II (if applicable) to the protocol are located in the Trial Master File.

Content: Global key staff and Country key staff

Protocol Amendment
no 1
to Protocol, final version 1.0
dated 25 March 2014

Trial ID: NN8640-4054

A multicentre, multinational, randomised, parallel-group, placebo-controlled (double blind) and active-controlled (open) trial to compare the efficacy and safety of once weekly dosing of NNC0195-0092 with once weekly dosing of placebo and daily Norditropin[®] FlexPro[®] in adults with growth hormone deficiency for 35 weeks, with a 53-week extension period

Trial phase: 3a

Applicable to all countries

Amendment originator:

[REDACTED]

This ~~confidential~~ document is the property of Novo Nordisk. ~~No unpublished information contained herein may be disclosed without prior written approval from Novo Nordisk. Access to this document must be restricted to relevant parties.~~

2 **Table of contents "Double click to update Table of Content"**

	Page
3	
4 1 Introduction including rationale for the protocol amendment	3
5 2 Changes to protocol version 1	6
6 3 Changes to Subject information/informed consent for version 1.....	36
7 4 Changes to Subject information/informed consent for pregnant partner version 1	42
8 5 Changes to Subject information/informed consent for male partner version 1	43

10 **1 Introduction including rationale for the protocol amendment**

11 This amendment is based on consultations with the Food and Drug Administration (FDA) in the US
12 and the Pharmaceuticals and Medical Devices Agency (PMDA) in Japan.

13

14 **1.1 The changes required by the FDA and PMDA**

- 15 • FDA: The primary analysis of the primary endpoint will be changed to an analysis based on the
16 ITT principle rather than on an assumption of missing at random. The former primary analysis
17 will be used as a secondary analysis (section 17)
- 18 • FDA: A general focus on the avoidance of missing data (sections 6, 8.2 and 8.6, introduction of
19 the SI/IC)
- 20 • FDA: Additional antibody and PK sampling will be added to align with the time points for
21 immunogenicity assessments as recommended in the FDA Immunogenicity guideline of
22 February 2013 (sections 2, 8.4.3 and 8.5.14)
- 23 • FDA: Inclusion of subjects with diabetes mellitus in order to understand the effect of the drug in

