369 ~~DM should be reported as an AE and treatment should be considered for DM at investigator's~~
370 ~~discretion. Discontinuation of the trial drug should only be considered if continued treatment is~~
371 ~~judged by the investigator to be a hazard for the subject. Increase in glucose is observed when~~
372 ~~starting GH replacement in some subjects and is often transient.~~

373 **8.5.7 8.5.6 Fasting plasma glucose, fasting insulin, and HbA1c**

374 Fasting plasma glucose, fasting insulin, and HbA1c tests will be assessed at screening and every 2
375 to 3 months throughout the trial (see section 2). Subjects must be fasting 8 hours before sample
376 collection, with only water allowed. If the subject comes to a fasting visit in a non-fasting state this
377 needs to be recorded in the eCRF.

378 *Rescue criterion for subjects diagnosed with diabetes mellitus before inclusion into the trial: If the*
379 *HbA1c increases clinically significantly during the trial, the investigator should consider adjusting*
380 *the anti-diabetic medication according to local practice.*

381 **8.5.9 8.5.8 Adrenocorticotrophic hormone (ACTH) stimulation test**

382 Cortisol levels will be assessed at screening, at the end of the two titration periods and at the start of
383 the extension period (see section 2). If a subject is not treated with glucocorticoid replacement an
384 ACTH stimulation test will be performed at screening if not performed within 3 months prior to
385 planned randomisation, at the end of the two titration periods and at the ~~end of the main trial~~ start of
386 the extension period.

387 ~~8.5.13~~ 8.5.12 Local tolerability

388 *Local tolerability will be evaluated on a regular basis at visits to the trial site (see section 2). If*
389 *suspicion of an injection site reaction occurs between site visits the subject should be instructed to*
390 *call the site as soon as possible for further guidance. An unscheduled visit may take place at the*
391 *investigators discretion.*

392 *At all site visits or specific unscheduled visits* Local tolerability will be evaluated by the
393 investigator by visual and manual inspection of injection sites.

394 *If a local tolerability reaction is identified* ~~based on the following assessments, and~~ the following
395 results will ~~also~~ be recorded in the eCRF:

396 ~~8.5.14~~ 8.5.13 Anti-drug antibodies

397 Anti-drug antibodies will be assessed at randomisation, 2, 4, 8 and 16 weeks after randomisation

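### Anti-diabetic medication can be changed because HbA1c rises, but the planned glycaemic summaries neither count these changes nor report by diabetic status

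*Protocol*

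**What the plan says.** Amendment 1 (section 1.1) admitted subjects with diabetes at the FDA's request: "Inclusion of subjects with diabetes mellitus in order to understand the effect of the drug in" this subgroup. It also made diabetic status a stratification factor (Protocol 5.1 and 11).

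Two routes then allow anti-diabetic treatment to change during the trial:

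- Protocol 8.5.6 sets a rescue criterion limited to subjects whose diabetes was known before they entered. When their "HbA1c increases clinically significantly during the trial, the investigator should consider adjusting" their diabetes treatment in line with local practice. It gives no HbA1c threshold, timing or drug class.
- Protocol 6.6.1, criterion 4, requires treatment to stop when an exclusion condition develops, but exempts "development of diabetes mellitus during the course of the trial that can be controlled with standard therapy". The Japan-specific amendment removes this exemption there, and Japan excludes diabetes at entry (6.3, criterion 16).

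Protocol 17.4.1.2 lists changes from baseline in fasting glucose, fasting insulin, HOMA estimates and HbA1c as safety endpoints. Their planned analysis is one sentence: "All other safety endpoints will be analysed using descriptive statistics". The SAP adds text on TRIM-AGHD and body weight only. It cites protocol version 6.0, which is not supplied as a clean text, but none of the supplied amendments adds a rule for these endpoints.

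The data for a fuller analysis exist. Under 8.3.3, "Changes in concomitant medication must be recorded at each visit as they occur", with dose and start and stop dates.

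**The concern.** A reading taken after anti-diabetic medication is started or raised reflects trial drug plus that medication. The change is prompted by the outcome being measured. If the drug raises HbA1c, adjustments should be more frequent on it than on placebo, and the difference in mean change shrinks towards zero. The direction is plausible: Protocol 3.1.5 and 12.6 name raised blood sugar and insulin among the most common adverse events so far.

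What is at stake is the question that diabetic subjects were enrolled to answer. No glycaemic output by diabetic status is planned, and even the exploratory interactions for the primary endpoint (17.3) cover only sex, region and GHD onset type. The number of subjects needing new or more anti-diabetic medication is a direct sign of a glycaemic effect, and it has no table.

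**Working it through.** The plan gives no figure for this point, so there is none to reproduce. Only the arm sizes come from the documents: 112 on NNC0195-0092 and 56 on placebo (Protocol 17.1). All other inputs are assumptions, shown as ranges.

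**1. Shift in the mean HbA1c change within the NNC0195-0092 arm (pre-existing diabetes)**

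Assume 5–15% of the arm has diabetes, 20–40% of these have medication raised, and this lowers HbA1c by 0.3–0.6 points.

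- Diabetic subjects: 112 × 0.05 = 5.6 to 112 × 0.15 = 16.8.
- Understatement among them = share adjusted × lowering: 0.2 × 0.3 = 0.06 to 0.4 × 0.6 = 0.24 points.
- Understatement in the whole arm = that × share with diabetes: at most 0.24 × 0.15 = 0.036 points.

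**2. Loss in the difference between NNC0195-0092 and placebo**

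Loss = q × (rA − rP) × m, where q is the share with diabetes, rA and rP are the shares of diabetic subjects adjusted on NNC0195-0092 and placebo, and m is the lowering. Wider assumptions: q 2–20%; rA/rP of 20%/5% or 50%/10%; m 0.5–1.0.

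- Whole arms: 0.02 × 0.15 × 0.5 = 0.0015 to 0.20 × 0.40 × 1.0 = 0.08 points. At q = 5%, about 0.004 to 0.02.
- Among diabetic subjects: 0.15 × 0.5 = 0.075 to 0.40 × 1.0 = 0.4 points.
- Equal adjustment rates (50%/50%): zero.

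**3. Precision, for scale**

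Assume an HbA1c SD of 0.3 to 0.5.

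- Whole arms: SE = SD × √(1/112 + 1/56) = 0.05 to 0.08.
- Diabetic stratum at q = 5% (5.6 versus 2.8 subjects): SE = SD × √(1/5.6 + 1/2.8) = 0.22 to 0.37.

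The stratum means will be noisy, so a simple count is more informative there.

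**4. New-onset diabetes**

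Steps 1 and 2 leave this route out. One treated subject with a lowering of 0.6 shifts the arm mean by 0.6/112 = 0.005 points. Such a subject has no diabetes at baseline, so the count must cover both strata.

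**5. How to handle values after a change**

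Illustration (assumed): 30% are adjusted, with a rise of 0.8 that treatment brings down to 0.3; the other 70% rise by 0.1.

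- Without adjustment: 0.3 × 0.8 + 0.7 × 0.1 = 0.31.
- All values: 0.3 × 0.3 + 0.7 × 0.1 = 0.16.
- Dropping adjusted subjects after the change: 0.10.
- Carrying their last value before the change, if that is the full 0.8: 0.31.

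Dropping the later values removes the subjects who rose most, and here it understates more than the all-values table does.

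**The case against.** The strongest reply is that the signal already has a planned output by arm. Protocol 12.1 counts a clinically significant laboratory abnormality that needs active management as an adverse event and gives a change of medicine dose as an example. Section 8.3.2 requires clinically significant worsening of a concomitant illness to be reported as one. Section 17.4.1.2 tabulates adverse events by treatment, with numbers and percentages of subjects. This stands in part. An HbA1c rise that leads to adjustment should appear there. But reporting rests on the investigator's judgement, tables by system organ class and preferred term do not show whose medication was started or raised, and they leave the HbA1c means as they are.

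The affected group is also narrow. Inclusion criterion 10 admits only diabetes with HbA1c below 7.0%, stable oral treatment, no history of injectables and no related co-morbidities. The endpoints are descriptive, with no confirmatory test, and an all-values summary is a legitimate description of the treatment as used. All of this stands and limits the weight of the point.

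A reader might infer more: that the summaries treat post-change values as if nothing had happened, and that the signal is masked most in the arm where it is largest. The documents do not support this. Section 17.4.1.2 is silent on such values; it does not say how they are used. The adjustment rates by arm, on which any differential masking depends, are not given, and with equal rates the difference loses nothing. The rule in 8.5.6 also covers only pre-existing diabetes, not every subject whose HbA1c rises.

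**Conclusion.** The gap is real but modest. Anti-diabetic treatment can change in response to the outcome, and no planned summary accounts for this or reports by diabetic status. Among diabetic subjects the attenuation could matter: 0.06 to 0.24 points within the NNC0195-0092 arm, or 0.075 to 0.4 points in the difference from placebo under the wider assumptions. In whole-arm means it is probably negligible: under 0.04 points in the first set, and 0.08 only at the extreme of the second, where it is no larger than the upper standard error. All of these rest on assumed prevalence, adjustment rates and treatment effect. The conclusion that does not depend on them is that the plan contains no glycaemic output aimed at the reason given for enrolling subjects with diabetes.

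**What to change.** In Protocol 17.4.1.2, or in the SAP, add by arm and by baseline diabetic status:

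- (a) the number and percentage of subjects who start or intensify anti-diabetic medication after first dose, taken from the concomitant medication data;
- (b) the change-from-baseline summaries of HbA1c, fasting glucose, fasting insulin and HOMA using all values, supplemented by a summary in which each subject whose medication was changed contributes the last value before the change, rather than dropping out of later visits.

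The cost is a few extra tables from data already collected; 8.5.6 schedules these measurements every 2 to 3 months, so values before a change should usually exist. Numbers in the diabetic stratum will be small. The last-value summary is only an approximation: it can understate a rise that would have continued and overstate one that would have passed. The clinical rescue rule is not changed.

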The estimates and standard deviations for the 100 data sets are pooled to one estimate and associated standard deviation for each treatment comparison using Rubin's formula:

$$m_{MI} = \frac{1}{100} \sum_{i=1}^{100} m_i, \quad SD_{MI} = \sqrt{\frac{1}{100} \sum_{i=1}^{100} SD_i^2 + \left(1 + \frac{1}{100}\right) \left(\frac{1}{100-1}\right) \sum_{i=1}^{100} (m_i - m_{MI})^2},$$

where m_i and SD_i are the estimated means and standard deviations for the 100 copies of the dataset, and m_{MI} , SD_{MI} are the pooled estimates.

From m_{MI} and SD_{MI} , the treatment difference at Week 34 between NNC0195-0092 and placebo will be estimated and the corresponding 95% CI and p-value will be calculated. As a secondary comparison, the treatment difference at Week 34 between NNC0195-0092 and Norditropin[®] FlexPro[®] will be estimated and the corresponding 95% CI will be calculated.

Superiority of NNC0195-0092 over placebo will be considered confirmed if the upper boundary of the two-sided 95% CI of the treatment difference (NNC0195-0092 – placebo) is below 0 (i.e. greater reduction from baseline in truncal fat percentage in the NNC0195-0092 treated group than in the placebo treated group).

The secondary comparison, comparison of NNC0195-0092 with Norditropin[®] FlexPro[®], will be used to assist the clinical judgment of the clinical relevance of the estimated treatment difference between NNC0195-0092 and placebo.

A secondary analysis of the primary endpoint based on an assumption of missing at random (MAR) will be done using an ANCOVA model with treatment (i.e. NNC0195-0092, placebo and once-daily Norditropin[®] FlexPro[®]), GHD onset type (adult or child), sex, region, DM and sex by region by DM interaction as factors and baseline truncal fat (%) as a covariate. From the model the treatment difference at Week 34 between NNC0195-0092 and placebo will be estimated and the corresponding 95% CI and p-value will be calculated. Subjects without Week 34 data for the

endpoint will not be included in the analysis. As a secondary comparison, the treatment difference at Week 34 between NNC0195-0092 and Norditropin[®] FlexPro[®] will be estimated from the model and the corresponding 95% CI will be calculated.

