Let δ be defined as the difference between the mean of the observed data and the mean of the unobserved data $\mu_{\text{unobs}} - \mu_{\text{obs}}$, adjusted for other observed data. Under an MAR analysis, δ is assumed to be 0. Positive values of δ indicate that subjects with missing endpoint values have smaller reductions from baseline than subjects with observed endpoint values. If subjects primarily withdraw due to perceived lack of efficacy then this could be the most likely direction of departure from MAR though change in truncal fat percentage may not be a parameter that is linked in a simple way to the perceived efficacy level of the individual subject. Let f_1 and f_0 be the fractions of subjects with unobserved endpoint data in the NNC0195-0092 and placebo arms, respectively. The sensitivity analysis is done by adding a quantity Δ to the treatment effect estimate under the MAR assumption (i.e. treatment effect estimate from the secondary analysis of the primary endpoint), where $\Delta = f_1\delta$ if data depart from MAR in the NNC0195-0092 arm only, $\Delta = -f_0\delta$ if data depart from MAR in the placebo arm only, and $\Delta = (f_1 - f_0)\delta$ if data depart from MAR in the same way in both arms. The calculations will use a range of δ values going from 0 to 2% and the approximation that the standard error of the treatment difference is unaffected by the sensitivity analysis²⁹. All subjects from the FAS can be viewed as included in this analysis as subjects with missing endpoint data will be contributing to one of the fraction values f_1 and f_0 . A similar sensitivity analysis will be made for the secondary comparison between NNC0195-0092 and Norditropin[®] FlexPro[®].

Other exploratory analysis of the primary endpoint

Using the same model as were used for the primary analysis of the primary endpoint, additional exploratory analysis will be done by including treatment by sex, treatment by region and treatment by GHD onset type interaction terms, one at a time, to the model. For region, sub group analysis will also be done based on the primary analysis model.

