604 unobserved data $\mu_{\text{unobs}} - \mu_{\text{obs}}$, adjusted for other observed data. Under an MAR analysis, δ is assumed
605 to be 0. Positive values of δ indicate that subjects with missing endpoint values have smaller
606 reductions from baseline than subjects with observed endpoint values. If subjects primarily
607 withdraw due to perceived lack of efficacy then this could be the most likely direction of departure
608 from MAR though change in truncal fat percentage may not be a parameter that is linked in a
609 simple way to the perceived efficacy level of the individual subject. Let f_1 and f_0 be the fractions of
610 subjects with unobserved endpoint data in the NNC0195-0092 and placebo arms, respectively. The
611 sensitivity analysis is done by adding a quantity Δ to the treatment effect estimate under the MAR
612 assumption (*i.e. treatment effect estimate from the secondary analysis of the primary endpoint*),
613 where $\Delta = f_1\delta$ if data depart from MAR in the NNC0195-0092 arm only, $\Delta = -f_0\delta$ if data depart from
614 MAR in the placebo arm only, and $\Delta = (f_1 - f_0)\delta$ if data depart from MAR in the same way in both
615 arms. The calculations will use a range of δ values going from 0 to 2% and the approximation that
616 the standard error of the treatment difference is unaffected by the sensitivity analysis³². All subjects
617 from the FAS can be viewed as included in this analysis as subjects with missing endpoint data will
618 be contributing to one of the fraction values f_1 and f_0 . A similar sensitivity analysis will be made for
619 the secondary comparison between NNC0195-0092 and Norditropin[®] FlexPro[®].

620 ~~Truncal fat percentage as a function of time since baseline is expected to be monotone if the subject~~
621 ~~stays on the randomised treatment in the main trial period. Based on this assumption, a sensitivity~~
622 ~~analysis using a multiple imputation technique will also be conducted where the trajectory after a~~
623 ~~withdrawn subject's last observation is imputed based on data from the placebo arm, thus~~
624 ~~mimicking an intention to treat (ITT) scenario where withdrawn subjects are assumed to be~~
625 ~~switched to no treatment (placebo) after withdrawal. For each of 100 copies of the dataset~~
626 ~~(seed=34247), an analysis of covariance model with GHD onset type, sex and region as factors, and~~

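### The delta sensitivity analysis in section 17.3 never lets a placebo-arm departure from MAR count against NNC0195-0092, so it has an adverse case but not the most adverse one

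*Protocol*

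**What the plan says.** The current text is the part of Protocol section 17.3 headed Sensitivity analyses. Amendment 1, section 2.11, has the same wording. Neither the later amendments shown nor the SAP changes it.

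- **Definition.** δ is the mean of the unobserved data minus the mean of the observed data, adjusted for other observed data. A positive value means that "subjects with missing endpoint values have smaller reductions from baseline than subjects with observed endpoint values".
- **Scenarios.** A shift Δ is added to the MAR estimate from the secondary analysis. Write f1 and f0 for the fractions without endpoint data in the NNC0195-0092 and placebo arms. When only the NNC0195-0092 arm departs, the shift is +f1δ. When only placebo departs, it is -f0δ. The third shift, (f1 - f0)δ, applies "if data depart from MAR in the same way in both arms".
- **Range.** δ takes "values going from 0 to 2% and the approximation that" the standard error does not change.
- **Reason for the sign.** Positive δ is put forward as perhaps the likeliest direction if subjects withdraw mainly because they perceive too little effect, "though change in truncal fat percentage may not be a parameter that is linked in a simple way to the perceived efficacy level".
- **Direction of benefit.** Superiority requires that the upper 95% limit for NNC0195-0092 minus placebo "is below 0 (i.e. greater reduction from baseline in truncal fat percentage in the NNC0195-0092 treated group". A positive Δ is therefore adverse to the drug.

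A similar analysis is planned against Norditropin.

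**The concern.** The reason given for δ ≥ 0 is cautious in the NNC0195-0092 arm and favourable in the placebo arm. If placebo subjects without a Week 34 scan did worse than those observed, the true placebo mean is worse than the MAR estimate and the drug looks better. The direction that would hurt the drug is the reverse: missing placebo subjects with larger reductions than observed ones. That is negative δ, outside the planned range. It appears neither alone nor combined with positive δ in the NNC0195-0092 arm.

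Negative δ is plausible on the protocol's own terms. Section 17.3 doubts the assumed direction. It also treats withdrawal criterion 2 and discontinuation criteria 6 and 7 as missing completely at random, and calls MAR questionable for the other withdrawal criteria and for withdrawal at will. Section 6.6.2 has only three withdrawal criteria, so the one left is use of weight-loss medication. One would expect subjects withdrawn for that reason to lose more fat, not less (my inference; the protocol does not say so).

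At stake is what the check can be said to show. Section 17.3 presents it as a test of robustness to departures from MAR, but for placebo it displays only the favourable side.

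**Working it through.** **Inputs.** Difference 2.5, SD 4.5, two-sided 5%, 104 and 52 completers, and drop-out of 7% or 15% (section 17.1); δ up to 2 (section 17.3). Two assumptions are mine: missingness is equal by arm, and every drop-out lacks a Week 34 value, so f1 = f0 = 0.07 or 0.15.

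**Plan's own figure.** The delta analysis states no numerical result. The two-sample t-test power with 104 and 52 is 0.902, matching the stated 90% and the 0.902 in the SAP's sample size output.

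**General shift.** With arm-specific values, Δ = f1δ1 - f0δ0. The planned scenarios are (δ, 0), (0, δ) and (δ, δ) with δ ≥ 0. The corner (δ, -δ) gives Δ = (f1 + f0)δ and is not among them.

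**Shifts at |δ| = 2**
- 7% missing: NNC0195-0092 only, 0.07 × 2 = +0.14; placebo only, -0.14; both alike, 0; opposite, (0.07 + 0.07) × 2 = +0.28. Placebo only with δ = -2 would give +0.14.
- 15% missing: +0.30; -0.30; 0; opposite +0.60. Placebo only with δ = -2 would give +0.30.

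**Upper 95% limits if the MAR estimate is exactly -2.5**
- 7%: SE = 4.5 × √(1/104 + 1/52) = 0.764; the estimate must be below -1.510 to be significant; MAR upper limit = -2.5 + 1.510 = -0.990.
- 15%: 112 × 0.85 ≈ 95 and 56 × 0.85 ≈ 48; SE = 4.5 × √(1/95 + 1/48) = 0.797; critical estimate -1.575; MAR upper limit = -0.925.

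| Case | 7% missing | 15% missing |
|---|---|---|
| NNC0195-0092 only (planned) | -0.850 | -0.625 |
| Placebo only (planned) | -1.130 | -1.225 |
| Both alike (planned) | -0.990 | -0.925 |
| Opposite (not planned) | -0.710 | -0.325 |

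All stay below 0. In the opposite case significance goes at δ of about 0.990/0.14 ≈ 7 (7%) or 0.925/0.30 ≈ 3 (15%).

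**Chance of losing significance at the design effect.** P(keep) = Φ((critical - Δ + 2.5)/SE).
- 7%: 0.9024 at Δ = 0, 0.8670 at 0.14, 0.8236 at 0.28. Joint probability of being significant and then losing it: 3.5% against 7.9%. Given a significant MAR result (divide by 0.9024): 3.9% against 8.7%.
- 15%: 0.8770, 0.7834 at 0.30, 0.6581 at 0.60. Joint: 9.4% against 21.9%. Conditional: 10.7% against 25%.

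**Where the omission changes the answer.** The planned worst case must still pass and the opposite case fail. The MAR upper limit must then lie between about -0.28 and -0.14 (7%) or -0.60 and -0.30 (15%).

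**Unequal missingness.** With f1 = 0.10 and f0 = 0.05, the planned worst shift is 0.20 and the opposite one 0.30. With f1 = 0.05 and f0 = 0.10, they are 0.10 and 0.30.

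**The case against.** The strongest reply is that no confirmatory conclusion rests on this check. It supports the secondary MAR analysis. Superiority is judged on the primary analysis, which already imputes missing NNC0195-0092 values from the placebo arm and uses scans taken at withdrawal. This stands, and it keeps the point minor. It does not close the gap: the same imputation makes missing placebo subjects resemble observed ones, so an adverse placebo departure is not tested there either.

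The second reply is that nothing is hidden. Δ is linear in δ, and the plan assumes that "the standard error of the treatment difference is unaffected by the sensitivity analysis". The placebo case at -2 is thus the planned placebo-only shift with its sign reversed, and the opposite corner is the sum of the two one-arm shifts in absolute value. This also stands. A reader might infer that the plan cannot detect sensitivity to missing placebo data; that is too strong. What is missing is the adverse case as a planned and reported result.

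Two other readings go too far:
- That the arms always move together. Two of the three scenarios involve one arm only, and the NNC0195-0092-only scenario is adverse to the drug.
- That only one scenario can weaken the result. The both-alike scenario is adverse whenever f1 > f0, though by less than the NNC0195-0092-only one, and the protocol does not guarantee balanced drop-out.

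Finally, the plan gives a reason for its sign. That reason is conditional, the plan itself qualifies it, and it is conservative in one arm only.

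**Conclusion.** The point holds as a minor gap. With δ limited to 0 to 2%, a placebo-arm departure never counts against NNC0195-0092. The plan contains an adverse case but not the most adverse one within its own magnitude of δ. With equal missingness the omitted shift is twice the largest planned one: 0.28 against 0.14 points at 7%, and 0.60 against 0.30 at 15%.

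A reader might infer that the trial's conclusion is at risk. The documents do not support that. At an estimate of -2.5 no case within |δ| ≤ 2 reverses significance, and the check bears on a secondary analysis. The omission matters for a borderline MAR result, and more so if missingness exceeds the planned 7%.

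The figures rest on the design effect and SD, on equal missing fractions taken from the overall drop-out rates, and on the plan's fixed standard error.

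**What to change.** In section 17.3, replace the three formulas by Δ = f1δ1 - f0δ0, with δ1 and δ0 each running from -2% to 2%. Report the full grid, including the corner δ1 = 2%, δ0 = -2%. The three planned scenarios remain as lines within it. For NNC0195-0092 versus Norditropin, show the same grid descriptively, because that comparison has no superiority criterion and so no defined adverse corner.

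The cost is a larger table and a less favourable worst-case figure. No new data, visits or subjects are needed, and the primary analysis is untouched.
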